A Lead fragment could result in the formation of a granuloma or infection. Although the occurrence of a fragment-related infection or granuloma is uncommon an infection may require removal of the Lead fragment and/or treatment with antibiotics. Investigators at the Cleveland FES Center and Case Western Reserve University have over 30 years of experience with dozens of research participants and hundreds of implanted leads like those used in this study. Infections and granulomas of leads or lead fragments have been uncommon, which is attributed to the materials and procedures that have been developed as well as the extensive experience of the Investigators..

5) Risks associated with lead fragment removal

It is possible that a Lead fragment or fragments may be retained in the body following removal of the Sprint MicroLead. If the Investigator determines that a lead fragment has been retained, the Investigator will instruct the subject and his/her caregiver to carefully inspect the Sprint MicroLead exit site and the surrounding skin in the weeks subsequent to Lead removal. Subjects will be instructed to contact the Investigator if there are any signs of pain, redness, swelling, discharge, or the appearance of a pimple-like mass (skin abscess). Such signs indicate that the fragment has migrated to the skin surface. At that time, if clinically warranted, the fragment may be removed via an outpatient procedure which involves lancing the abscess and removing the fragment and application of a topical antibiotic.

The risks associated with the Lead fragment removal procedure include discomfort during the procedure and skin irritation or infection in the area of the retained fragment. These risks are rare. The risk of infection is

mitigated by instructing the subject and/or his caregiver to carefully monitor the site and immediately report any signs of infection.

6) Risk of Lead Replacement due to Lead Migration or Lead Becoming Dislodged

It is possible that the Lead may migrate from its original intended location or that the Lead may become dislodged (i.e. come out completely) during the treatment phase. This risk is rare. If lead migration occurs, it is possible that the subject may experience discomfort during stimulation (described further below under "risk of discomfort with electrical stimulation"). If the Lead has migrated substantially or has come out, it may be necessary to place another Lead. Each time an additional lead is placed, the subject has an additional exposure to the same risks of lead placement described above in "risk of needle insertion for Sprint MicroLead placement".

This risk of lead migration or the becoming dislodged is mitigated by instructions to the subject and their caregiver, as appropriate, to ensure careful handling of the Lead and Lead Connector during bandage changes. In addition, the risk of placing a new lead is further mitigated by ensuring that Investigators are trained in the lead placement procedure, ensuring that the shoulder tissue appears healthy prior to placing a new lead, and collecting an additional INR blood sample for subjects who are taking warfarin.

7) Risk of skin irritation under the Sprint Pad or bandages

It is possible that the skin could become irritated under the Sprint Pad. Additionally, there may be skin irritation in the area surrounding the Lead insertion site, where an adhesive bandage is taped to the skin. This risk is common; however, the bandages can be changed to prevent the irritation from returning.

The risks of skin irritation under the Sprint Pad (a modified surface electrode) and under the bandages surrounding the Sprint MicroLead exit site will be reduced by excluding patients with known sensitivity to skin surface electrodes and/or medical-grade adhesive tapes. Subjects and their caregivers will be advised to examine the electrode exit site at regular intervals to look for any signs of irritation. To avoid irritation under the Sprint Pad, subjects will be advised that the Sprint Stimulator and Sprint Pad may be moved to slightly different locations near the Lead insertion site throughout the treatment phase. In addition, subjects will be instructed to avoid placing the Sprint Pad or bandages on unhealthy skin.

8) Risk of mechanical or electrical failure of the Sprint Stimulator

There is a rare chance that the Sprint Stimulator may malfunction. It is very unlikely that a stimulator malfunction will be harmful. If there is a problem with the Sprint Stimulator or the Sprint MicroLead, the Stimulator will reset itself such that no stimulation is delivered.

The Sprint Stimulator will not deliver stimulation if it detects a high impedance level indicating a broken lead wire or a faulty lead connection. Subjects will be instructed to contact study staff in the event that an error message is displayed.

9) Risks for pregnant women

The risk of harm to a pregnant woman or fetus is unknown. The device will not be used in any subjects known to be pregnant. If a subject is known to become pregnant during the treatment phase, stimulation will be stopped and the Sprint MicroLead will be removed.

Potential risks of pregnancy will be reduced by administering a pregnancy test in females of reproductive potential at study enrollment. Additionally, the Informed Consent form will advise subjects that the risks of electrical stimulation during pregnancy are unknown and that they should immediately notify the Investigator if they suspect they have become pregnant during the study.

10) Risk of discomfort due to electrical stimulation

Intramuscular electrical stimulation may be perceived by the subject as a tingling or vibrating sensation, which may feel uncomfortable or painful. The risk of discomfort due to stimulation is uncommon. At high stimulation intensities, shoulder pain may worsen.

To minimize the risk of increased shoulder pain as the result of high intensity stimulation, the Investigator will set an appropriate intensity for the stimulation. Should a subject feel pain as the result of stimulation, he or she will be able to turn off the stimulation using the Sprint Stimulator controls. Although muscle fatigue is unlikely with six hours of daily stimulation therapy, subjects may also feel some discomfort if muscle fatigue occurs. If muscle fatigue is observed, the Investigator is able to prescribe several shorter stimulation sessions totaling six hours per day.

Discomfort or pain due to stimulation may occur if the Sprint MicroLead migrates from its original location. Stimulation near the skin surface may be perceived as a "pins and needles" or stinging sensation and may be uncomfortable.

The risk of pain due to a migrating electrode will be minimized by leaving stimulation off until the Sprint MicroLead has had time to stabilize. The Sprint MicroLead has a fine wire barb. In addition, the proximal portion of the Lead exits the skin which makes this Lead more susceptible to becoming dislodged during bandage changes. As a conservative measure, we allow one week for encapsulation of the Sprint MicroLead to ensure stability. Data on the Lead has shown that electrodes are fully encapsulated by the surrounding tissue.

A tingling sensation may be felt under the Sprint Pad but this sensation is not expected to be uncomfortable. If discomfort or pain is felt at the Sprint Pad site, the subject will be instructed to turn off stimulation and move the Sprint Pad and Stimulator to a different location.

11) Risks associated with Diathermy

There is a risk of tissue damage if a subject undergoes diathermy. Shortwave or microwave diathermy is a therapy that may be used to apply deep therapeutic heat for the treatment of selected medical conditions such as relief of pain, muscle spasms, and joint contractures. Diathermy can cause excessive heating of any implanted metal part (including Leads), resulting in serious injury. The risk of tissue damage associated with diathermy is rare.

The risk of diathermy will be reduced by informing subjects that diathermy must not be used. In addition, subjects will be informed to never undergo diathermy if a Sprint MicroLead fragment remains in the body.

12) Risks associated with MRI

Tissue damage may occur if a subject undergoes an MRI procedure while the Sprint MicroLead, or a fragment of the Sprint MicroLead, is in the body. The risk of tissue damage associated with MRI use is rare.

Should a subject require a scheduled MRI during the treatment phase, the Sprint MicroLead will be removed. The decision to remove any remaining fragments will depend on a careful assessment of the benefits of the MRI, risks of MRI with retained fragments and risks associated with removing of electrode fragments.

13) Risk of allergic reaction to local anesthetics and/or risk of accidental injection of local anesthetic into a vein

There is a risk that the subject may have an allergic reaction to the local anesthetic used during the treatment phase prior to insertion of the Sprint MicroLead. If the subject were to have an allergic reaction, it would usually happen while the subject was still in the clinic. If a subject complains of itching, difficulty breathing, lightheadedness and dizziness, or a swollen tongue (common signs of an allergic reaction), appropriate medical treatment will be administered. The risk of allergic reaction to local anesthetics is rare. In addition, there is a risk of adverse central nervous system and/or cardiovascular effects (including a rare risk that the

subject's heart can stop beating or that they could stop breathing) if the local anesthetic is administered improperly.

The risks of allergy to local anesthetic agents will be reduced by excluding subjects with a prior known history of allergy or sensitivity to local anesthetic agents. In addition, prior to the procedure, subjects will be advised of the signs and symptoms of an allergic reaction. Because subjects will be awake during this procedure, they will be able to verbalize any itching or other signs of allergy to the local anesthetic. The risks of accidental intravascular injection of local anesthetic will be reduced by careful administration of the local anesthetic. Careful administration includes ensuring that a vein has not been punctured by the syringe prior to injecting the anesthetic and observing the subject after the injection. In addition, the physical location of the anesthetic injection (in the deltoid) combined with the injection technique would rarely result in an accidental intravascular injection.

14) Risk associated with venipuncture (if applicable)

The risks of drawing blood from a vein include discomfort at the site of puncture, possible bruising and swelling around the puncture site, an infection, and faintness from the procedure. The risks of discomfort, bruising, and swelling around the puncture site are common while the risks of infection and fainting are rare. Blood sample collections are only required in subjects taking warfarin.

Subjects taking warfarin are at greater risk for developing bruises following venipuncture. However, the risk of discomfort and bruising at that puncture site will be reduced by applying gentle pressure following venipuncture as is the standard practice for collection of blood samples. The rare risk of infection due to venipuncture will be reduced by using proper blood collection technique including wiping the puncture site with an appropriate cleansing solution.

Some subjects may experience a vasovagal ("fainting") response due to the discomfort of needle insertion or anxiety associated with the procedure. The risk of fainting will be reduced by observing subjects during and following venipuncture to ensure that they feel comfortable rising from their seated position. Subjects with a history of vasovagal responses will be supine during venipuncture.

15) Risk of worsening of pain symptoms

It is possible that the subject may have a worsening of pain symptoms or that they may not obtain any therapeutic benefit from the treatment. The risk of worsening pain symptoms is uncommon. In addition, subjects will have the opportunity to discontinue treatment if their stimulation is too uncomfortable.

These risks are mitigated by clinical training on the safe limits. Subjects do not have access to make changes to the programming controls and thus could not advertently change the value.

16) Risks of Outcomes Assessments

The questionnaires and Fugl-Meyer Assessment present no risks. The assessments of shoulder torque and kinematics may be slightly uncomfortable. The measures of central sensitization (mechanical pain thresholds for hyperalgesia, pinprick pain thresholds for hyperalgesia, temporal summation of repetitive pin-prick stimuli) may be slightly uncomfortable and may cause brief skin irritation. The optional measures (tactile/touch, vibration and thermal/thermal pain detection thresholds, temporal summation of repetitive thermal stimuli, and Conditioned Pain Modulation (CPM)) also may be uncomfortable and may cause brief skin irritation.

17) Other

Some of the survey questions present a rare risk of psychological harm.

When PHI is involved there is the rare risk of a privacy breach.

There may be other risks as yet unknown.

10.6

Are there defined stopping rules? Yes No

Describe in enough detail for the IRB to assess safety.

What are the stopping rules for the study? What are the conditions under which a subject will be withdrawn from the study for safety reasons, i.e. disease progression?

The study could be terminated at any time for valid scientific reasons or reasons related to the protection of subjects participating in this study. A reason for study termination includes but is not limited to the discovery of an unexpected, significant, or unacceptable risk to the participants enrolled in the study.

What findings, events, or conditions would require a research subject to be removed from the study? (i.e. disease progression)

The research subject may be removed if they develop any condition during the course of the study which would preclude the safe use of stimulation or otherwise impair their safe participation in any study activity.

10.7 **What Category of risk will study participants be exposed too?**

Name

Psychological

Physical

Privacy

Should be consistent with risks listed in the Consent Form.

10.8 **If Other listed above please specify:**

A text box is provided for further explanation.

Describe the availability of medical or psychological services that participants might require as a consequence of participation in this the research:

A text box is provided for further explanation.

10.9

It is not expected that participants would require medical or psychological services as a consequence of participation in this research. If that were to occur, appropriate referrals would be made for the subject.

10.10 **Describe in detail any measures in place to minimize or protect against the exposure of study subjects to these risks:**

1) Risks associated with needle insertion for Sprint MicroLead placement

To minimize the risks associated with percutaneously placing fine wire leads, only appropriately trained physician investigators will perform the procedure. In addition, the risk of excessive bleeding will be reduced by excluding candidates who are taking warfarin with an INR > 3.0 and by placing manual pressure on the implantation site until hemostasis is achieved. Finally, the risk of discomfort during the procedure will be reduced by the use of an appropriate amount of local anesthetic.

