Protocol: Peripheral Nerve Stimulation for Shoulder Pain: Dose Response

ID: IRB16-00510

NCT02928055

Document Date: 12/18/2020

8.0 Methods and Procedures I:

8.1 Will this research involve the following Social-Behavioral Procedures:

Check all that apply.

Name _____
 Psychological Testing _____
 Surveys/Questionnaires _____

8.2 Will this research involved any of the following Medical Procedures/Considerations:

Check all that apply.

Name _____
 Collection of Biohazardous Substances _____
 Study of Human Biological Materials (i.e. Urine Collection) _____
 Investigation/Approved Devices _____
 Study of Existing Data _____
 Medical Tests, Comparisons, Evaluations _____
 Clinical Assessments (EEG, EKG, SCID, etc.) _____
 Venipuncture (Blood Draw) _____
 Use of investigational devices _____
 Psychological testing _____

8.3 Identify Data Collection types for this study:

Check all that apply.

Name _____
 Audio-Recording/Video-Recording/Photographs _____
 Chart Review - Prospective _____
 Existing/Retrospective Data/Specimens _____
 Interviews, questionnaires or psychological tests _____

Note if you are doing, recordings, Video-Recording/Photographs then subjects will need to sign the MetroHealth Audio-Video Consent form. See the IRB Forms and Templates.

View: 08-01 Methods and Procedures II

8.1 Methods and Procedures II:

8.4 * Please specify in detail the methods and procedures that are involved in this research:

If this field is not completed your protocol will not be reviewed. Do not enter N/A. Please describe what methods and procedures will be involved in this research.

Study Summary: This is a pilot RCT to explore the role of muscle contraction as a mechanism produced by peripheral nerve stimulation (PNS) to reduce hemiplegic shoulder pain (HSP). Thirty subjects will enroll and receive a 3-week course of percutaneous IM PNS at one of 3 doses. Subjects will be randomized to receive the standard IM PNS treatment (15,120 total contractions), IM PNS at half the standard dose (7,560 total contractions), or IM PNS at 1.5 times the standard dose (22,680 total contractions). Dose will be controlled by differing the stimulation time per day (3h, 6h, or 9h) while keeping constant the duty cycle of stimulation. Subjects will be followed for 12 weeks after treatment.

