PNS Treatment Protocol: After one week for lead stabilization [80], the Sprint PNS System will be programmed for stimulation. Based on over 30-yrs of experience, the Cleveland FES Center established parameters for safe and effective delivery of PNS (pulse frequency = 12 Hz; pulse amplitude = 20 mA; pulse duration = 5-200 usec (set by clinician); duty cycle = 5-sec ramp-up, 10-sec plateau, 5-sec ramp down, 10 sec off; daily stim time (randomized) = 3, 6, 9 hrs/day; total contraction dose (randomized) = 7560, 15120, 22680 contractions). [81] These parameters provide strong fused comfortable muscle contraction with minimal fatigue. [6-12, 49, 62, 71,82-84] Stimulation frequency and amplitude are fixed. The pulse duration is set to produce strong, comfortable contraction of both the middle and posterior deltoids. A balanced biphasic waveform allows an equal amount of current to flow in either phase, creating a safe net zero charge. [85] In this dose-response study, participants receive 3h, 6h, or 9h of stimulation each day. The stimulator keeps an electronic log for compliance monitoring.

Electrode and Electrode Site Surveillance and Electrode Removal: All caregivers and participants will be trained in the assessment of electrode site and the daily placement of the Sprint Pad. The caregiver conducts daily inspections to detect complications. The nurse coordinator inspects the site for infection and performs motor/sensory threshold testing for lead migration and lead integrity, respectively, at the following times: within 48-72 hrs of lead placement, at the beginning of PNS treatment, and at the end of treatment. Inspection and testing of motor/sensory thresholds and impedance may also occur anytime during the 3-wk PNS treatment period as deemed necessary. At the end of treatment, the electrode is removed by gently pulling on the external portion. All participants undergo radiographic surveillance for retained electrode fragments.

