8.5 Does this study only involve the use of existing/retrospective data/specimens?

Check yes or no.

No

8.6 Describe in detail the study design also known as the experimental flow. Include all study procedures a subject will go through, in order of sequence and timing, including frequency of visits, duration of visits, length of subject participation etc. Please Note this needs to be written for an educated person who is not an expert in the field, do not exceed 300 words:

This is also known as NIH Experimental Procedure section or Clinical Trial Procedure/Experimental Flow section. Do not just attach documents in response to this question you must do a study design summary for IRB Review.

The duration of each subject's participation will be ~4 months.

Visit 1 – Consent/Eligibility: Consent form signed; assessed for eligibility per inclusion/exclusion criteria; MMSE administered; BDI, PCS & FABQ administered; medical history, demographics, comorbidities, and medication use recorded; blood drawn for INR (in applicable subjects); pregnancy test (in applicable subjects). (~3.5 hrs)

Visit 2 – Baseline Outcomes Assessment: Study outcome measures (see Outcomes Assessment) administered to establish baseline levels. (~4 hrs)

Visit 3 - Sprint MicroLead (Electrode) Implant Procedure: Testing of muscle response with Sprint Test Needles; Implantation of percutaneous Sprint MicroLead. Subject given instructions on care of Lead exit site. Skin checked, subject queried for medication usage. Randomization to treatment group. Subset of study outcome measures (questionnaires only) administered. (~2.5 hrs)

Visit 4 - 48-72 hour Post-Implant Safety Check: Check the Lead exit site within 48-72 hours of the Implant procedure; dressing changed. (~1 hr)

Visit 5 - Start of Stimulation: Collection of parameter data; programming of external stimulator (Sprint Stimulator). Subject given instructions on use of System and care of Lead exit site. Skin checked, dressing changed, subject queried for medication usage and adverse events. Subset of study outcome measures (BPI-SF only) administered. (~2 hrs)

Phone Call #1 – One week after starting stimulation, subject queried on condition of Lead exit site, pain, adverse events. (30 min)

Phone Call #2 – Two weeks after starting stimulation, subject queried on condition of Lead exit site, pain, adverse events. (30 min)

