21.23 How will this medical device be used in research?

Percutaneous PNS System: The Sprint PNS System (SPR Therapeutics, Cleveland, OH) will be used to deliver the PNS therapy. The System consists of a small external stimulator, percutaneous lead, and pad. The external stimulator "snaps" on to the pad. The pad has an embedded power source for the System but also serves as the anode. The pad is replaced regularly based on treatment parameters, allowing the investigative team to prescribe the total dosage based upon the number of pads. The single-channel stimulator outputs a biphasic current waveform with current pulse parameter ranges that are suitable for PNS. These electrodes have been used extensively to deliver percutaneous PNS to shoulder muscles. [6-12,62,71]

Give a brief description.

Lead Placement Procedure:

The procedure will be performed under a sterile condition. The location and depth of the electrode implant site are determined by monopolar needle stimulation with demonstration of strong contraction of both the middle and posterior deltoid muscles. [6,9,62,70] The introducer loaded with the lead is inserted perpendicular to the skin surface and advanced to the depth (3-4 cm) defined by the monopolar test stimulation. The introducer is then withdrawn with the electrode retained in the muscle by a barb at its tip.

PNS Treatment Protocol:

After one week for lead stabilization [80], the Sprint PNS System will be programmed for stimulation. Based on over 30-yr of experience, the Cleveland FES Center established parameters for safe and effective delivery of PNS (pulse frequency = 12 Hz; pulse amplitude = 20 mA; pulse duration = 5-200 usec (set by clinician); duty cycle = 2-sec ramp-up, 16-sec plateau, 2-sec ramp down, 10 sec off; daily dose = 6 hrs/day). [81] These parameters provide strong fused comfortable muscle contraction with minimal fatigue. [6-12,49,62,71,82-84] Stimulation frequency and amplitude are fixed. The pulse duration is set to produce strong, comfortable contraction of both the middle and posterior deltoids. A balanced biphasic waveform allows an equal amount of current to flow in either phase, creating a safe net zero charge. [85] In this dose-response study, participants receive 3h, 6h, or 9h of stimulation each day. The stimulator keeps an electronic log for compliance monitoring.

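### The muscle-fatigue provision offers a six-hour daily total that fits only the 6 h arm, and sections 8.4 and 21.23 give different waveforms for the same treatment

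*Protocol*

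**What the plan says.** Section 8.4 (Study Summary) makes daily stimulation time the randomised factor: "Dose will be controlled by differing the stimulation time per day (3h, 6h, or 9h) while keeping constant the duty cycle of stimulation". The PNS Treatment Protocol in the same section gives totals of 7,560, 15,120 and 22,680 contractions for 3, 6 and 9 h per day.

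The fatigue provision is in section 10.5, item 10 (discomfort due to electrical stimulation). It opens with a premise: "Although muscle fatigue is unlikely with six hours of daily stimulation therapy, subjects may also feel some discomfort if muscle fatigue occurs". The remedy follows: "If muscle fatigue is observed, the Investigator is able to prescribe several shorter stimulation sessions totaling six hours per day". The same two sentences appear in section 10.10 (measures to protect against risks), section 3.B.1 of the data safety monitoring plan, and section 21.24 (complications). None of the four copies names an arm or gives a version for 3 h or 9 h.

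The waveform is given twice:

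- Section 8.4, PNS Treatment Protocol: "duty cycle = 5-sec ramp-up, 10-sec plateau, 5-sec ramp down, 10 sec off".
- Section 21.23, PNS Treatment Protocol: "duty cycle = 2-sec ramp-up, 16-sec plateau, 2-sec ramp down, 10 sec off; daily dose = 6 hrs/day".

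Later in its own paragraph, section 21.23 says that participants receive 3, 6 or 9 h each day. On delivered dose, section 8.4 adds: "The stimulator keeps an electronic log for compliance monitoring".

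**The concern.** The arms differ only in hours per day, so any instruction that resets those hours acts on the randomised factor itself. The only stated remedy for fatigue resets them to a single figure, the standard arm's. The 9 h arm has the longest daily exposure, yet the text that calls fatigue unlikely speaks only of six hours.

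A 9 h participant handled this way would still be counted in the high-dose arm while receiving the standard daily dose. In a comparison by assigned arm, that narrows the top dose step and pulls the dose response towards flat. The log would show the reduction afterwards but would not restore the contrast.

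The waveform matters for another reason. The trial explores muscle contraction as the mechanism of pain relief, so the contraction should be defined once. Two sections describe it differently and the document does not say which governs.

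**Working it through.** **1. Reproduce the stated doses.** Inputs from section 8.4: cycle 5 + 10 + 5 + 10 = 30 s; 3, 6 or 9 h per day; three weeks = 21 days.

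Contractions per hour = 3600 / 30 = 120. Total = 120 × hours per day × 21.

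- 3 h: 120 × 3 × 21 = 7,560
- 6 h: 120 × 6 × 21 = 15,120
- 9 h: 120 × 9 × 21 = 22,680

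All three match the protocol.

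**2. Apply the fatigue provision as written, one participant.** The daily count becomes 120 × 6 = 720 in every arm. The assigned counts are 360 (3 h), 720 (6 h) and 1,080 (9 h). A 9 h participant therefore loses 360 per day. Read literally, a 3 h participant would gain 360 per day, which is double the assigned dose.

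For a 9 h participant, total = 120 × (9 × d + 6 × (21 − d)), where d is the number of days before the switch:

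| Switch | Total | Loss | Share of assigned 22,680 |
|---|---|---|---|
| From day 1 (d = 0) | 15,120 | 7,560 | 67% |
| After day 7 | 17,640 | 5,040 | 78% |
| After day 14 | 20,160 | 2,520 | 89% |

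The daily dose equals the standard arm's from the day of the switch. The three-week total equals it only for a switch on day 1.

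**3. Arm level.** Assume 10 per arm (30 / 3). The planned 9 h versus 6 h difference is 22,680 − 15,120 = 7,560. One switched participant lowers the high-arm mean by loss / 10:

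- From day 1: 756; 756 / 7,560 = 10%
- After day 7: 504; 504 / 7,560 = 6.7%
- After day 14: 252; 252 / 7,560 = 3.3%

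Against the 9 h versus 3 h difference of 15,120, these shares halve to 5%, 3.3% and 1.7%.

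Fatigue must first be observed. In section 8.6 the first scheduled contact after stimulation starts is the one-week phone call and the next is at two weeks, although unscheduled visits are possible. The 6.7% and 3.3% figures are therefore the more realistic ones, and 10% is the bound.

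**4. Waveforms side by side.**

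| | Section 8.4 | Section 21.23 |
|---|---|---|
| Ramp-up / plateau / ramp-down / off (s) | 5 / 10 / 5 / 10 | 2 / 16 / 2 / 10 |
| Cycle (s) | 30 | 30 |
| On time (s) | 20 | 20 |
| Contractions per hour | 120 | 120 |
| Plateau per contraction (s) | 10 | 16 |
| Plateau hours per day, 3 / 6 / 9 h arm | 1.0 / 2.0 / 3.0 | 1.6 / 3.2 / 4.8 |

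Counts, on/off fraction and the 1:2:3 arm ratio agree. Plateau time per contraction is 60% longer in 21.23 (16 / 10 = 1.6).

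**The case against.** The strongest reply is that the sentence is leftover six-hour wording and not an instruction to cut anyone's dose. It directly follows a remark about six hours of daily therapy, and in that setting it means splitting a six-hour prescription with the total unchanged. It is permissive and sits in risk text, while sections 8.4 and 21.23 both assign 3, 6 or 9 h and describe prescribing total dose through the number of pads. The literal doubling for a 3 h participant shows that nobody would apply it blindly. The four appearances are one text repeated: 3.B.1 and 21.24 are marked as carried over from 10.5.

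Much of this stands. The repetition adds no weight, and the provision obliges nobody to reduce a dose. What remains is that six hours is the only total the fatigue text offers, including in 10.10, where it serves as the protective measure. No other text tells the investigator to keep the assigned hours when fatigue appears. For a 9 h participant, moving to six hours is a plausible use of that permission.

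A reader might infer that the high arm would lose 10% to 30% of its separation from the standard arm. The documents do not support that. It needs one to three of ten participants switched on day 1, and no fatigue rate is given. Section 8.4 describes fatigue as minimal with these parameters. The nearest frequency, discomfort due to stimulation, is classed in 10.5 as uncommon, which that section defines as above 1% up to 10%. That class is specific neither to fatigue nor to nine hours, but it gives no ground for assuming several in ten.

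It is also fair to say that rewording cannot restore dose where a participant truly cannot tolerate nine hours. It helps only those who could complete nine hours in split sessions.

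On the waveform, a reader might infer bias between arms or a different contraction dose. Neither follows: counts and on/off fraction are identical, and one setting used throughout affects all arms alike.

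**Conclusion.** The point holds as a wording defect that touches the randomised factor, and it should be fixed. The fatigue provision was not adapted to three arms and preserves the assigned dose only at 6 h. No bias has been shown, since any effect depends on an investigator using the permission for a participant outside the 6 h arm.

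With 10 per arm assumed, the cost is about 6.7% of the planned 9 h versus 6 h contraction difference for each 9 h participant switched after the one-week call, and 3.3% after week 2. Ten per cent is the ceiling per participant, and the cost is nil if no one is switched. These are shares of the planned contraction difference, not of any effect on pain. Confidence is high on the wording and low on whether the situation would arise.

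The waveform mismatch is a separate and smaller matter: the contraction is not uniquely defined on paper (10 s or 16 s plateau). Section 8.4 looks like the updated text because its parameter list carries the randomised hours, but that is an inference. The six-hour daily dose left in 21.23 is corrected within its own paragraph and needs only tidying.

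**What to change.** - **Fatigue provision (10.5, 10.10, 3.B.1, 21.24).** Say that the shorter sessions add up to the participant's assigned daily hours (3, 6 or 9 h). Allow any further reduction needed for tolerance or safety, and record it as a dose deviation with its start date.
- **Waveform (21.23).** Align with 8.4 on one setting, after checking it against the parameter data collected at Visit 5, when the stimulator is programmed.
- **Daily hours (21.23).** Replace the fixed six hours in the parameter list with 3, 6 or 9 h per day.

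The cost is one sentence corrected in four copies, one parameter line, and a check of data already collected for at most 30 participants. If treatment is already complete, the stimulator log and the Visit 5 data would show whether any 9 h participant was reduced and which waveform was used.
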